7.8.4.3 Multicenter Studies

This is a single arm study, and thus no arms-sites interaction will be analyzed.

7.8.4.4 Multiple Comparison/Multiplicity

Not applicable in this study.

7.8.4.5 Use of an "Efficacy Subset" of Subjects

Not applicable in this study.

Page 29 of 43 05 October 2018

7.8.4.6 Active-Control Studies Intended to Show Equivalence or Non-Inferiority

Not applicable in this study.

7.8.4.7 Examination of Subgroups

Analysis set:

Full analysis set

Analysis variable(s):

Office trough sitting diastolic blood pressure (change at the End of Treatment Period I)

Office trough sitting systolic blood pressure (change at the End of Treatment Period I)

Proportion of subjects who achieved the target blood pressure (at the End of Treatment Period I)

Stratum:

Gender [Male, Female]

Type of hypertension [Essential hypertension, Secondary hypertension]

RAS inhibitors (ACE inhibitors, ARB, and DRI) prior to Run-in Period [Yes, No]

Antihypertensive drugs at the start of Treatment Period I [Yes, No]

eGFR (mL/min/1.73 m²) $[Min \le - \le 59, 60 \le - \le 89, 90 \le - \le Max]$

Analytical Method(s):

The following analysis (1) will be performed for office trough sitting diastolic and systolic blood pressures by each stratum. The following analysis (2) will be performed for the proportion of subjects who achieved the target blood pressure by each stratum.

- (1) Summary statistics
- (2) Frequency distributions

7.9 Pharmacokinetic/Pharmacodynamic Analysis

7.9.1 Pharmacokinetic Analysis

Analysis set:

Subjects who underwent proper determination of plasma concentrations of TAK-536 in the "full analysis set"

Analysis variable(s):

Plasma concentrations of TAK-536 and its metabolites (M-I and M-II)

Visit:

Week 2 (predose), Week 2 (postdose), Week 4 (predose), Week 4 (postdose), Week 8 (predose), Week 8 (postdose), Week 12 (predose), Week 12 (postdose), and Week 16 (postdose)

Analytical method(s):

The following analysis (1) will be performed for the above analysis variables by weight group ($< 50 \text{ kg}, \ge 50 \text{ kg}$) and in the combined weight groups. The dose immediately before the blood sample collection for plasma concentrations will be used. The following analysis (2) will be performed in the combined weight groups.

- (1) Summary statistics and CV (%) by dose at each visit
- (2) A scatter plot for TAK-536 plasma concentration at Week 2 (predose) and changes in office sitting blood pressure (diastolic and systolic) at the same visit will be presented.

7.9.2 Pharmacodynamic Analysis

Not applicable in this study.

7.10 Other Outcomes

Not applicable in this study.

7.11 Safety Analysis

The safety endpoints are the primary endpoints in this study.

7.11.1 Adverse Events

7.11.1.1 Overview of Treatment-Emergent Adverse Events

Analysis set:

Safety analysis set

Analysis variable(s):

TEAE

Categories:

Relationship to study drug [Related, Not related]

Intensity [Mild, Moderate, Severe]

Analytical method(s):

The following summaries will be provided for the above analysis variables by weight group ($< 50 \text{ kg}, \ge 50 \text{ kg}$) and in the combined weight groups.

(1) Overview of TEAE

- 1) All TEAEs (number of events, number and percentage of subjects)
- 2) Relationship of all TEAEs to study drug (number of events, number and percentage of subjects)
- 3) Intensity of all TEAEs (number of events, number and percentage of subjects)
- 4) TEAEs leading to study drug discontinuation (number of events, number and percentage of subjects)
- 5) Serious TEAEs (number of events, number and percentage of subjects)
- 6) Relationship of serious TEAEs to study drug (number of events, number and percentage of subjects)
- 7) Serious TEAEs leading to study drug discontinuation (number of events, number and percentage of subjects)
- 8) TEAEs resulting in death (number of events, number and percentage of subjects)

TEAEs will be counted according to the rules below:

[Number of subjects]

• In case of "summaries by relationship to study drug"

A subject with occurrences of TEAE in both categories (i.e., Related and Not related) will be counted once in the Related category.

• In case of "summaries by intensity"

A subject with multiple occurrences of TEAE will be counted once for the TEAE with the maximum intensity.

• In case of summaries other than the above

A subject with multiple occurrences of TEAE will be counted only once.

[Number of events]

For each summary, the total number of events will be calculated.

7.11.1.2 Displays of Treatment-Emergent Adverse events

Analysis set:

Safety analysis set

Analysis variable(s):

TEAE

Categories:

Intensity [Mild, Moderate, Severe]

Time of onset (day) $[1 \le - \le 14, 15 \le - \le 28, 29 \le - \le 42, 43 \le - \le 56, 57 \le - \le 70, 71 \le - \le 84, 85 \le - \le Max]$ $[1 \le - \le 84, 85 \le - \le 168, 169 \le - \le 252, 253 \le - \le 336, 337 \le - \le 420, 421 \le - \le Max]$

Analytical method(s):

The following summaries will be provided for the above analysis variables using frequency distributions by weight group ($< 50 \text{ kg}, \ge 50 \text{ kg}$) and in the combined weight groups.

TEAEs will be coded using MedDRA and will be summarized based on SOCs and PTs. SOCs will be sorted alphabetically and PTs will be sorted in decreasing frequency for tables provided by SOC and PT. SOC and PT will be sorted in decreasing frequency for tables provided by SOC only or PT only.

See "9.0 APPENDIX" for definitions of the TEAEs related to hypotension and renal dysfunction.

- (1) All TEAEs by SOC and PT
- (2) All TEAEs by SOC
- (3) All TEAEs by PT
- (4) Drug-related TEAEs by SOC and PT
- (5) Intensity of all TEAEs by SOC and PT
- (6) Intensity of drug-related TEAEs by SOC and PT
- (7) TEAEs leading to study drug discontinuation by SOC and PT
- (8) Serious TEAEs by SOC and PT
- (9) All TEAEs by SOC and PT over time
- (10) TEAEs related to hypotension by SOC and PT
- (11) TEAEs related to renal dysfunction by SOC and PT
- (12) Non-serious TEAEs whose incidence summarized by PT is \geq 2% by SOC and PT

The frequency distribution and incidence will be provided according to the rules below:

[Number of subjects]

- In case of "summaries by SOC and PT, by SOC only, or PT only"
 - A subject with multiple occurrences of TEAE within a SOC will be counted only once in that SOC. A subject with multiple occurrences of TEAE within a PT will be counted only once in that PT. Also, when calculating the percentages for TEAEs, the number of subjects in the safety analysis set will be used as the denominator.
- In case of "summaries of intensity by SOC and PT"

A subject with multiple occurrences of TEAE within a SOC or a PT will be counted only once for the TEAE with the maximum intensity. Also, when calculating the

percentages for TEAEs, the number of subjects in the safety analysis set will be used as the denominator.

• In case of "summaries by SOC and PT over time"

A subject with a TEAE that occurs in more than one interval is counted in all the intervals that the TEAE occurs. For each time interval, a subject with multiple occurrences of TEAE within a SOC or a PT will be counted only once in that SOC or PT. When calculating the percentages of TEAEs for each time interval, the number of subjects at risk (i.e., "subjects who either have an exposure to study drug or have an occurrence of TEAE, during or after the corresponding time interval") will be used as the denominator. The number of subjects whose "onset of any one of the TEAEs is within the time interval" will be used as the numerator.

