When the antihypertensive drugs are required dose reduction or interruption because of the concerns in tolerability with titration (i.e., excessive reduction in blood pressure, other AE, etc.) in the Treatment Period II, the antihypertensive drugs other than TAK-536 (in case of concomitant use) should be reduced or interrupted first. Thereafter, dose reduction or interruption of TAK-536 should be considered.

[figure not shown]
(4) Follow-up Period

Follow-up Period will be 2 weeks from the next day of the final dose of TAK-536. Safety will be evaluated at Week 54 after the start of the Treatment Period.

At the time when the data from approximately 25 subjects are collected, the data until Week 12 in the Treatment Period will be analyzed. In addition, at the time when all subjects complete Week 24 in the Treatment Period, the data until Week 24 in the Treatment Period will be analyzed separately after being locked. These analyses will not intend to continue or discontinue this study.

A schematic of the study design is included as Figure 6.a. A schedule of assessments is listed in Appendix A.

Figure 6.a Schematic of Study Design

- 1) The subjects whose blood pressures meet the inclusion criteria 1 (at earliest) week after receiving placebo in the Run-in Period can enter the Treatment Period. For the subjects only who treated with any antihypertensive drugs as a prior treatment only, the Run-in Period could be extended up to 4 weeks if blood pressures do not meet the inclusion criteria.
 - 2) If subjects have difficulty in discontinuing antihypertensive drugs completely at the start of the Run-in Period, the antihypertensive drugs can be down-titrated concurrently with administration of placebo. In the case of the down-titration, antihypertensive drugs should be discontinued at least 1 week (7 days) before the start of the Treatment Period I. Especially, beta-blockers (BBs) should be tapered off gradually since sudden discontinuation of BBs may cause withdrawal syndrome.
 - 3) In the Treatment Period I, TAK-536 can be titrated biweekly when the subjects do not achieve the target blood pressure while evaluation of safety and tolerability. TAK-536 can be reduced at the investigator's or subinvestigator's discretion if there are any concerns in tolerability with titration of TAK-536 (i.e., in case of occurring any AEs caused by titration of TAK-536).

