9.3.5 Final Visit or Early Termination

The Final Visit will be performed on Week 52 or at the Early Termination Visit.

The tests and observations specified for each visit will be performed.

For subjects early terminate the study after the start of the Treatment Period, if possible, the same tests, observations, and evaluations as those scheduled at Week 52 should be performed.

Whenever possible, office sitting blood pressure should be determined within 3 days after early termination and the other tests, observations, and evaluations should be performed within 14 days after early termination (the next day of the final dose should be calculated as the first day).

For all subjects who entered the Treatment Period, the investigator or subinvestigator must complete the Subject Status on eCRF page with the first day when the subjects received the study drug for the Treatment Period and study completion or early termination status until Week 24 and study completion status at Week 52 for subjects who continuingly received the study drug beyond Week 24.

9.3.6 Follow-up Period: Week 54

Follow-up Period will begin the first day after the final administration of TAK-536 for the Treatment Period and will continue until 2 weeks. The tests and observations specified for each visit will be performed. If subjects terminate the study drug in the Run-in Period or at an early stage of the Treatment Period, no tests, observations, and evaluations will be required but care should be taken for subject safety.

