10.2 Procedures

10.2.1 Collection and Reporting of AEs

10.2.1.1 AE Collection Period

Collection of AEs will commence from the time the subject signs the informed consent. Routine collection of AEs will continue until the end of the Follow-up Period (or the tests performed at early termination).

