7.0 METHODS OF ANALYSIS AND PRESENTATION

7.1 General Principles

7.1.1 Study Definitions

- Day of last observation/test or contact, whichever comes later: Last date of SDTM.SV
- Treatment-emergent adverse event (TEAE): Any AE occurring after the first study drug administration for the Treatment Period
- Pretreatment event (PTE): Any AE occurring after obtaining informed consent but before the first study drug administration for the Run-in Period
- Adverse event during the Run-in Period: For subjects who enter the Treatment Period, any
 AE occurring after the first study drug administration for the Run-in Period until the first
 study drug administration for the Treatment Period. For subjects who do not enter the
 Treatment Period, any AE occurring after the first study drug administration for the Run-in
 Period
- Summary statistics: Number of subjects, mean, standard deviation, maximum, minimum, and quartiles
- Duration of exposure to study drug for the Treatment Period: Date of the last study drug administration for the Treatment Period – Date of the first study drug administration for the Treatment Period + 1
- Study period after the study drug administration for the Treatment Period: Date of last observation/test or contact – Date of the first study drug administration for the Treatment Period + 1
- Compliance rate with the study drug for the Treatment Period: Total number of doses of study drug for the Treatment Period (Amount of study drug dispensed for the Treatment Period Amount of study drug returned for the Treatment Period) / Duration of exposure to study drug for the Treatment Period × 100 (rounded to 1 decimal place)
- Office trough sitting diastolic and systolic blood pressures on each measuring day: The mean of 3 values on a given measuring day (rounded to integers) is used as the representative value of that measuring day.

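### The at-risk count for TEAEs over time admits a child who has stopped drug only if that child has a TEAE, which modestly inflates some interval percentages

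*SAP*

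**What the plan says.** Protocol 13.1.5 lists TEAEs over time among the analyses of the primary (safety) endpoint. It is item (9) of SAP 7.11.1.2, by SOC and PT, for each weight group and combined. Two sets of onset bands are used: six 14-day bands to Day 84 followed by 85 to Max, and five 84-day bands to Day 420 followed by 421 to Max.

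For each band, the subjects at risk are "subjects who either have an exposure to study drug or have an occurrence of TEAE, during or after the corresponding time interval". The numerator is the number of subjects whose "onset of any one of the TEAEs is within the time interval".

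Three other provisions determine who can be observed off drug:

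- SAP 7.1.1 sets no upper time limit on a TEAE: "Any AE occurring after the first study drug administration for the Treatment Period".
- Protocol 10.2.1.1 continues AE collection after the last dose: "Routine collection of AEs will continue until the end of the Follow-up Period (or the tests performed at early termination".
- For completers, Protocol 6.1 states that the "Follow-up Period will be 2 weeks from the next day of the final dose of TAK-536". For early terminators, Protocol 9.3.5 asks that, where possible, "the other tests, observations, and evaluations should be performed within 14 days after early termination".

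The other SOC and PT tables in SAP 7.11.1.2 divide by the whole safety analysis set. SAP 7.12 includes item (9) in the Week 12 interim analysis of about 25 subjects, which supports the design for children under 6 and goes into regulatory consultation material.

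**The concern.** A denominator should contain everyone who could have had an event that the table would count. Here, children on drug qualify by exposure. Children off drug but still observed qualify only by having an event. Among the latter, each child with an event adds one to both numerator and denominator, and each child without an event adds nothing to either.

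At stake is the reading of event timing during titration, when children who stop because of poor tolerability may well be followed into the next 14-day band. The table is descriptive and no test depends on it. It is nevertheless a named summary of the primary endpoint, and at the interim its denominators will be small.

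**Working it through.** No figure in the plan depends on this rule, so there is nothing to reproduce first.

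**Algebra.** For one interval, let n be the children exposed in or after it and a those of them with an onset in it. Let m be the children who stopped earlier but are still routinely observed in it, and e those of the m with an onset.

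- SAP rule: (a + e)/(n + e)
- Observation-based: (a + e)/(n + m)

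Since e ≤ m, the SAP value is never the lower of the two. It is higher whenever a + e > 0 and e < m.

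**Which intervals are reached.** With 14 days of off-drug observation, a child reaches at most one band beyond the band of the last dose.

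- 14-day bands: every stop day from 1 to 84 reaches the next band.
- 84-day bands: only the 14 stop days before each of the boundaries at Days 84, 168, 252 and 336 do so, that is 4 × 14 = 56 of 364 stop days, or 15%.
- Completers: the last dose (about Day 364) and the Week 54 window (Days 373 to 386, SAP Table 7.a) both lie in band 337 to 420, so they are counted there through exposure.

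**Single examples (assumed counts).**

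- n = 45, a = 9, m = 3, e = 1: SAP 10/46 = 21.7%; observation-based 10/48 = 20.8%; on drug only 9/45 = 20.0%.
- Weight group, n = 20, a = 4, m = 3, e = 1: SAP 5/21 = 23.8%; observation-based 5/23 = 21.7%.
- Interim weight group, n = 10, a = 1, m = 2, e = 1: SAP 2/11 = 18.2%; observation-based 2/12 = 16.7%.

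**Expected excess.** Suppose the risk p is the same on and off drug. The observation-based percentage then has expectation p. Given e, the SAP percentage has expectation (np + e)/(n + e), which exceeds p by e(1 − p)/(n + e). The expected excess is therefore (1 − p) × E[e/(n + e)], with e binomial(m, p). For m = 1 it reduces to p(1 − p)/(n + 1). With n = 45 this is 0.05 × 0.95/46 = 0.10 points at p = 5% and 0.4 × 0.6/46 = 0.52 points at p = 40%. Excess in percentage points:

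| On drug (n) | Stopped, still observed (m) | p = 5% | p = 10% | p = 20% | p = 40% |
|---|---|---|---|---|---|
| 45 | 1 | 0.10 | 0.20 | 0.35 | 0.52 |
| 45 | 3 | 0.31 | 0.58 | 1.03 | 1.54 |
| 45 | 5 | 0.51 | 0.97 | 1.71 | 2.52 |
| 20 | 1 | 0.23 | 0.43 | 0.76 | 1.14 |
| 20 | 3 | 0.68 | 1.27 | 2.24 | 3.31 |
| 20 | 5 | 1.12 | 2.10 | 3.67 | 5.32 |

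If risk falls after stopping (n = 45, m = 3, 20% on drug, 2% to 10% off drug), the SAP rule gives 20.1% to 20.5% against a pooled 18.9% to 19.4%, a gap of 1.1 to 1.2 points.

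**The case against.** The best defence is that the effect is small and confined to one descriptive table. The numerators are right, and the overall, drug-related, serious, discontinuation, hypotension and renal tables use the full safety set. Fourteen days is also an upper limit. Early-termination tests close routine AE collection and may come sooner, and Protocol 9.3.6 waives follow-up assessments for children who stop early in treatment. Those are the children who matter for the 14-day bands, so m may be small. All of this stands and limits the size, but it does not justify the rule.

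A second defence is that the TEAE clause keeps every counted event inside the denominator. That is a real merit. It tells against a simple substitution of the SAP 7.1.1 variable "Study period after the study drug administration for the Treatment Period: Date of last observation/test or contact", because its end is the last date in the subject-visits dataset. A TEAE with onset after that date would be in the numerator but not the denominator.

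A reader might infer more than the documents support:

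- *That the error can only raise percentages.* Because the rule also admits events after the interval, a stopped child with an event beyond the routine window (for example a spontaneously reported SAE, Protocol 10.2.2) enters intervening intervals as event-free and slightly dilutes them. Against an on-drug denominator, a stopped child's event also lowers rows for other PTs: 5/45 = 11.1% becomes 5/46 = 10.9%.
- *That it creates a late rise.* Completers stay within band 337 to 420, and the 14-day bands end at Day 84.
- *That Day 421 to Max would show 100%.* One event with nobody exposed would give 1/1, but the last planned window closes at Day 386, so the band should normally be empty.

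Finally, if occurrence were read to include ongoing events, the upward effect would be smaller, but entry would still depend on having a TEAE.

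**Conclusion.** The concern holds in a limited form. The interval denominator depends on the outcome for children who have stopped drug, and no other provision corrects it. Relative to an observation-based denominator, the bias within the routine off-drug period is upward. The main places affected are the 14-day bands over Days 1 to 84, small weight groups and the Week 12 interim.

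The sizes of about 0.1 to 2.5 points (45 on drug), and up to about 5 points in a group of 20, rest on assumptions: 1 to 5 stopped children still observed per interval, interval risk of 5% to 40%, and equal risk on and off drug. The upper end needs five such children and 40% risk in one interval. The point does not call overall TEAE incidence into question. It is worth correcting because the table reports the primary endpoint and the correction is cheap.

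**What to change.** Rewrite the at-risk definition in SAP 7.11.1.2 so that it makes no reference to TEAE occurrence, and apply the same window to numerator and denominator. Either option works:

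- **(a) Observation-based.** Define each child's AE observation window as running from the first Treatment Period dose to the end of AE collection (end of Follow-up, or the early-termination tests). A child is at risk in an interval if this window reaches the start of the interval. Count only onsets inside the window, and list later-reported events separately.
- **(b) On-drug.** Restrict both numerator and denominator to children exposed in the interval, and show TEAEs after stopping in a separate row.

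Option (a) should use the end of AE collection rather than the last visit date, so that every counted event stays within the denominator. It will still count a child observed briefly in a long band, such as 85 to Max, as fully at risk, just as the present rule does for a child briefly exposed there.

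The cost is a short text change and one revised derivation. Interval percentages will differ slightly, and a few late events will move to a listing or a separate row.

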7.11.1.3 Displays of Pretreatment Events

Analysis set:

All subjects who signed the informed consent form

Analysis variable(s):

PTE

Analytical method(s):

The following analysis will be performed for the above analysis variables using frequency distributions.

PTEs will be coded using MedDRA and will be summarized based on SOCs and PTs. SOCs will be sorted alphabetically and PTs will be sorted in decreasing frequency.

- (1) All PTEs by SOC and PT
- (2) Serious PTEs by SOC and PT

The frequency distributions will be provided according to the rules below:

[Number of subjects]

A subject with multiple occurrences of PTE within a SOC will be counted only once in that SOC. A subject with multiple occurrences of PTE within a PT will be counted only once in that PT.

7.11.1.4 Displays of Run-in Adverse Events

Analysis set:

All subjects who received the study drug for the Run-in Period

Analysis variable(s):

AEs during the Run-in Period

Analytical method(s):

The following analysis will be performed for the above analysis variables using frequency distributions.

AEs during the Run-in Period will be coded using MedDRA and will be summarized based on SOCs and PTs. SOCs will be sorted alphabetically and PTs will be sorted in decreasing frequency.

- (1) All AEs during the Run-in Period by SOC and PT
- (2) Serious AEs during the Run-in Period by SOC and PT

The frequency distributions will be provided according to the rules below:

[Number of subjects]

A subject with multiple occurrences of AE within a SOC will be counted only once in that SOC. A subject with multiple occurrences of AE within a PT will be counted only once in that PT.

